Researchers are requesting a waiver of authorization to access medical record data. ORPRN study staff plan to conduct the chart audit at each clinic over the course of 1-3 days. Data will be stored on the OHSU instance of REDCap or stored securely on OneDrive and ORPRN staff and select Kaiser Permanente research team members will have access to the data by utilizing a password-protected file on OneDrive or a REDCap user login. OneDrive and REDCap user permissions will be matched to roles as described in the established Data Use Agreement between Kaiser Permanente and OHSU and to the IRB. PHI will never be disclosed outside of the study team and all PHI will be destroyed upon completion of the study. Through data use agreements, a limited dataset will be shared with the sponsor, the National Cancer Institute. The following data elements will be included in the limited data set: patient identifier, age group, sex, Hispanic or Latino origin, race, state of residence, county of residence and primary health insurance. When possible, the data set will also include primary language, ZIP code of residence, individual history of CRC, most recently performed screening test date and result, and diagnostic colonoscopy date and result.

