recruit clinics; conduct	exclusion criteria for CCOs and clinic	literature,	board on inclusion and exclusion	2020		
baseline assessment; use	participation in Phase II.	statistical power	criteria			
results from pilot to		requirements				
prepare to conduct a	b. Develop CCO and clinic	Relevant	Feedback from local advisory	Jan – Mar		
large-scale, pragmatic	recruitment materials	literature	board	2020		
implementation-	b. Successfully engage 3 CCOs and 30	Feasibility data	List of participating CCOs and	Mar – Sep		
effectiveness trial and	rural/frontier clinics for the main trial	from pilot study	selected clinic characteristics	2020		
scale-up (see Phase II).	d. Develop manual outlining trial	Feasibility data	Feedback from advisory board on	Apr – Sep		
	protocols (including quality assurance	from pilot study	recruitment materials; study	2020		
	protocols), scopes of work, and		protocol; scope of work			
	associated budgets.					

Aims	Assessment/	Data Sources	Description	Timeline
	Measurement			
Aim 1. Conduct a large-scale pragmatic study, cluster randomized control trial, to assess the implementation, effectiveness, and maintenance of the program piloted in Phase I in 30 rural primary care clinics (n ~ 3,960 patients aged 45 – 75) using practice facilitation to support implementation. Using a mixed methods approach, identify patient-, clinic/health system-, and payer/policy/community-level factors that are associated with reach, effectiveness, implementation and maintenance	Assessment of effectiveness (patient and clinic level).	Administrative data, claims data, EHR data from clinics, vendor data, laboratory data, survey data.	Patient Level Outcome (Primary): Completion of any CRC screening Clinic Level Outcome: Proportion of Medicaid patients screened for CRC We will compare the intervention vs. control clinics after adjusting for baseline at 6 and 12 months. The primary endpoint is 6 months. Secondary outcomes: completion of testing types (fecal testing, FIT-DNA, CT Colonography, Colonoscopy, Flex Sigmoidoscopy; patient level) and % completion (clinic level); time to screening from study-eligible patient list pull (patient level); FIT results (patient level); follow-up colonoscopy completion (patient level); time to colonoscopy from abnormal FIT result (patient level); and adenomas or cancers detected (patient level).	2021-Sep 2024

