The primary effectiveness outcome of this study at the patient level is the completion of any colorectal cancer (CRC) screening (for study-eligible patients). Consistent with the pragmatic nature of the trial, we will use claims, vendor data, and EHR data for calculating CRC screening outcomes. Comparing the likelihood of receiving CRC screening between intervention and usual care groups at 6-month post participant list-pull date, we hypothesize that CRC screening will be more likely in patients allocated to the intervention group versus the usual care group. To examine the effectiveness of the program CRC screening completion at 6 months, we will use the generalized form of the hierarchical linear model (HLM; using a logit link and binomial distribution, aka multilevel logistic regression) to account for the clustering of patients within clinics and the assignment to arm at the clinic level. The variables that will be included in the model are the clinic baseline screening rate (if available) and a binary indicator of arm (1=tailored, 0=standard) as fixed effects and clinic is a random effect. A positive and significant coefficient for arm would provide support for the effectiveness of the intervention. We will do a moderator analysis at all levels to explore the impact of patient and clinics characteristics (see outcomes table above), and implementation components affecting outreach on completion likelihood in groups of patients determined at analysis (e.g. never screened, Hispanic, etc.).

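### The primary 6-month model uses no patient-level baseline covariate, so some power is forgone and chance case-mix imbalance is at best partly corrected

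*Combined protocol and SAP*

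**What the plan says.** Section 9.0 (Phase II, Aim 1) analyses completion of any CRC screening at 6 months with a hierarchical model "using a logit link and binomial distribution, aka multilevel logistic regression". Its terms are given as a closed list: "The variables that will be included in the model are the clinic baseline screening rate (if available) and a binary indicator of arm", both entered "as fixed effects and clinic is a random effect". The Phase II table in section 8.0 restates the adjustment: "We will compare the intervention vs. control clinics after adjusting for baseline at 6 and 12 months". It adds no patient-level term.

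Patient characteristics appear in the analysis only through an exploratory moderator analysis, "in groups of patients determined at analysis (e.g. never screened, Hispanic, etc".

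On the available data:
- Section 7.0 lists, for the limited data set to be shared with the sponsor, "patient identifier, age group, sex, Hispanic or Latino origin, race, state of residence". It adds "most recently performed screening test date and result" only where this can be supplied.
- Section 4.0 excludes patients who are already current for screening.
- Section 7.0 describes a chart audit in intervention and control clinics. Section 10.2 extends chart review to everyone eligible for screening.

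**The concern.** Whether a patient has been screened before is a plausible strong predictor of screening in the next 6 months, and its frequency probably differs between clinics. Clinics are the randomized units and there are few of them, so the arms can differ on it by chance. The model as written has no patient-level term to absorb such a difference.

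Two things are at stake. One is power, in a trial whose Phase II plan states no power calculation. The other is how the result reads if the arms turn out visibly unequal in case-mix. Adjustment chosen after an imbalance is seen would be post hoc, and moderator groups settled at analysis cannot stand in for pre-specified adjustment.

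**Working it through.** **No plan figure to reproduce.** For Phase II the documents give no alpha, power, effect size, usual-care rate, intraclass correlation (ICC) or allocation ratio. They do give "in 30 rural primary care clinics (n ~ 3,960 patients aged 45 – 75", so 3,960/30 = 132 patients per clinic. The abstract gives about 4,500 patients, so 4,500/30 = 150. Everything else below is assumed.

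**Step 1: chance imbalance.** Take a binary patient characteristic with prevalence p, m patients per clinic, 15 clinics per arm and between-clinic correlation ICC_x:

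SD of the arm difference = sqrt(2p(1−p)[1 + (m−1)ICC_x] / (15m))

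- m = 150, p = 0.3, ICC_x = 0.02: sqrt(0.42 × 3.98 / 2,250) = 0.027
- m = 132, p = 0.5, ICC_x = 0.05: sqrt(0.5 × 7.55 / 1,980) = 0.044
- m = 132, p = 0.5, ICC_x = 0.10: sqrt(0.5 × 14.1 / 1,980) = 0.060

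Over p = 0.3 to 0.5 and ICC_x = 0.02 to 0.10 the SD is 2.7 to 6.0 percentage points, a 95% range of about ±5 to ±12 points.

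**Step 2: effect on the arm estimate before any correction.** The approximate shift in the arm log-odds ratio is log(OR_x) × imbalance, where OR_x is the covariate's odds ratio. With OR_x = 3 and a 1-SD imbalance:

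- 1.099 × 0.044 = 0.05
- 1.099 × 0.060 = 0.07

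In the OR_x = 3 scenarios of step 3, the planned model's standard error is 0.103 to 0.155. The clinic baseline rate, when used, removes part of this shift.

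**Step 3: power with the planned model type.** Random-intercept logistic models were simulated under these assumptions: 30 clinics of 132 patients, usual-care rate about 20%, arm OR 1.5, prior-screened share 50%, clinic baseline rate correlated about 0.5 with the clinic's screening propensity, two-sided 0.05 t test on between-clinic degrees of freedom, and 300 runs per scenario. ICC_y is the outcome ICC. Planned means arm plus clinic baseline rate; the comparison adds prior screening status.

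| ICC_y | ICC_x | OR_x | Power, planned | Power, with covariate | Gain (points) | Mean SE of arm log-OR |
|---|---|---|---|---|---|---|
| 0.03 | 0.02 | 2 | 85.7% | 86.3% | 0.6 | 0.119 → 0.121 |
| 0.03 | 0.05 | 2 | 85.0% | 86.7% | 1.7 | 0.121 → 0.121 |
| 0.03 | 0.05 | 3 | 82.7% | 86.7% | 4.0 | 0.122 → 0.124 |
| 0.03 | 0.10 | 3 | 82.7% | 86.3% | 3.6 | 0.127 → 0.124 |
| 0.06 | 0.05 | 3 | 65.3% | 66.0% | 0.7 | 0.155 → 0.158 |
| 0.01 | 0.10 | 3 | 92.3% | 98.7% | 6.4 | 0.103 → 0.096 |

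Monte Carlo error is about 2 points per power figure. Without the clinic baseline rate, the gain from the patient covariate is 0.3 to 9.0 points (for example 76.0% to 84.3%, and 88.0% to 97.0%). The clinic baseline rate alone adds 4.3 to 6.7 points over no adjustment.

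**Step 4: validity.** With no arm effect, the planned model rejected in 3.0 to 8.7% of runs and the model with the covariate in 4.0 to 8.3%. Some scenarios exceed 5% in both models, so omitting the covariate is not the cause.

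**Step 5: a second method.** A two-stage clinic-level analysis, with a clinic baseline covariate in both versions, used 4,000 replicates in each of six scenarios. Assumed inputs were usual-care rate 12 to 20%, arm OR 1.45, between-clinic variance 0.05 to 0.10 on the logit scale, 45% previously screened with a between-clinic SD of 10 points, and OR_x 2 to 3. Power rose by 2.2 to 5.7 points and the variance of the risk difference fell by 3.3 to 15.0%. This is not the planned model, but direction and broad size agree.

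**The case against.** The strongest reply is that nothing here is invalid. Randomization protects the comparison, and chance imbalance is already part of its standard error. That stands. A reader might infer that the primary estimate is biased or its type I error inflated; step 4 does not support this.

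A reader might also infer that case-mix imbalance goes wholly uncorrected. The sentence quoted from section 9.0 rules that out, because the clinic baseline rate plausibly absorbs part of any case-mix difference that affects screening. Randomization is also stratified on health system. But the rate is conditional on availability with no stated fallback, and it is a single clinic-level figure with no defined denominator, whereas the analysis set leaves out patients already current. It is a proxy at best.

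The data objection stands in part. The section 7.0 list describes the file for the sponsor rather than the analysis file, and it qualifies the prior test data. Section 7.0 also ties the claims transfer to clinics randomized to implement the intervention. On the other side, excluding current patients requires some look at screening history, never-screened patients are named as a moderator group, and charts are reviewed in both arms. So prior screening status should be obtainable, but it is not guaranteed complete. Knowing that a patient is not current is less than knowing whether the patient was ever screened.

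Finally, the gain comes from prior screening under chosen inputs. No separate gain was computed for age or sex, the two variables listed more firmly.

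**Conclusion.** The point holds as one of efficiency and robustness. The primary model leaves out patient-level baseline covariates that are listed (age group, sex) or should be obtainable (prior screening status). Chance case-mix imbalance is therefore corrected only in part, and only when the clinic baseline rate exists.

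With that rate in the model, the power gain is roughly 0.5 to 6 points: under 2 points in three of six scenarios, and 3.6 to 6.4 points in the three with OR_x = 3 and ICC_y of 0.03 or less. It is small where case-mix varies little between clinics. It need not appear as a smaller standard error of the log-odds ratio, which fell in only two of six scenarios, because adjustment also moves the conditional log-odds ratio away from zero.

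All sizes rest on assumed rates, correlations and covariate effects, and on 15 clinics per arm. The documents state none of these.

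**What to change.** In section 9.0, pre-specify age group, sex and prior screening status (never, previously, unknown) as fixed effects in the primary model, alongside arm and the clinic baseline rate. State that all three are taken as of the list-pull date from sources common to both arms, never from vendor or navigation records that exist only for intervention patients. Add that if prior screening status cannot be obtained comparably in both arms, adjustment is for age group and sex only.

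Keep the currently listed model as a named sensitivity analysis. Report a standardized risk difference so that the headline result stays on the same scale whichever covariates enter.

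The cost is a few sentences of analysis text, plus a check that screening history can be recovered alike in both arms. The odds ratio becomes conditional on more covariates, and prior screening status may be incomplete, which the unknown category only partly addresses.

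Two neighbouring gaps are separate and not closed by this change: no rule covers a missing clinic baseline rate, and health system, the stratification factor, is not among the model terms.

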In Phase II (Years 02-05), we will test our intervention using a two-arm cluster randomized control trial in 30 rural primary care clinics using program training and practice facilitation to support implementation. Participating clinics will be randomized into two groups: Intervention and Usual Care. Randomization will be stratified on health system. As in the pilot, the intervention combines: (1) a clinic-health planvendor supported direct-mail fecal testing program with targeted outreach for patients who have never been screened or who have yet to establish care and (2) patient navigation for those who are referred for colonoscopy as either the primary screening or for follow-up from an abnormal fecal test. We will evaluate effectiveness, implementation, and maintenance of the intervention through quantitative and qualitative measures. Results from the trial will inform scale-up of the program through partnerships with 20 regional and national organizations that serve rural/frontier primary care clinics using webinars, train-the-trainer workshops and collaborative learning activities.

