For this project, we expect to recruit at least three CCOs and 33 Oregon clinics, which allows up to a 10% attrition rate to achieve our target of 30 rural primary care clinics. Based on Census Bureau data (https://www.census.gov/quickfacts/or), as of 2017, Oregon residents are 50.4% female and 13.1% Hispanic or Latino. Also based on Census data, Oregon resident diversity consists of 2.2% African American, 1.8% American Indian or Alaskan Native, 0.4% Native Hawaiian and other Pacific Islander, 4.7% Asian, 87.1% white, and 3.8% two or more races. Based on the Census Bureau's data, we expect the participating individuals to make up a representative sample of Medicaid individuals across the state.

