#### 9.0 BIOSTATISTICAL CONSIDERATIONS

**Phase I:** Because this is the pilot phase, in which the primary purpose is to examine the feasibility and acceptability of the intervention and not to test a hypothesis, we have not performed a power analysis to determine the required sample size for this phase. Instead our primary goal was to evaluate the feasibility and acceptability of the program. 

Phase II, Aim 1 (Implementation-Effectiveness Trial): We will test our hypotheses using a two-arm cluster randomized control trial. Participating clinics will be randomized into two groups: Intervention and Usual Care. Randomization will be stratified on health system. Our study design aligns with the core principles of the PRECIS-2 framework. Our eligibility criteria are broad and consistent with the realities of rural primary care (e.g., small sample sizes, limited quality improvement capacity). Our patient recruitment approach for the direct mail and navigation programs is aligned with routine care and standard quality improvement approaches and requires no individual consent. Participating clinics will serve populations that display CRC screening disparities, and be diverse in terms of EHR, rural geographic locations, and populations served. Our intervention is flexible and is designed to be adapted according to payer and clinics' resources and preferences. Our primary outcome, completion of any CRC screening, is pragmatic and relevant to patients, clinics, and payers (CCOs), and our primary analysis follows the intention-to-treat concept. We will collect data 6 times from the CCOs. Data will be transferred every 6 months from the Spring of 2021 to the Fall of 2023 to be able to capture up to 18 months of follow-up following each mailing.

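### With about 30 clinics, the primary test has no stated level, reference distribution or small-sample method and omits the stratification factor, so its error rate is not assured

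*Combined protocol and SAP*

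**What the plan says.** The trial is a "two-arm cluster randomized control trial in 30 rural primary care clinics" (section 1.0). Section 4.0 plans to recruit "33 Oregon clinics, which allows up to a 10% attrition rate to achieve our target of 30 rural primary care clinics". Section 9.0 says "Randomization will be stratified on health system".

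For the primary outcome, section 9.0 specifies a hierarchical model "using a logit link and binomial distribution, aka multilevel logistic regression". Its terms are "the clinic baseline screening rate (if available) and a binary indicator of arm (1=tailored, 0=standard) as fixed effects and clinic is a random effect". Health system is not among them. The hypothesis is directional: "we hypothesize that CRC screening will be more likely in patients allocated to the intervention group versus the usual care group". The decision rule is "A positive and significant coefficient for arm would provide support for the effectiveness of the intervention".

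The documents give no significance level, sidedness, type of test, denominator degrees of freedom, estimation method or small-sample correction. There is no Phase II sample-size calculation, so they also give no intraclass correlation, control screening rate or clinic-size variation.

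**The concern.** Arm varies only between clinics, so the information on the arm effect is limited by the number of clinics, not the number of patients. With 30 clinics and three clinic-level parameters (intercept, arm, baseline rate) there are about 27 degrees of freedom. Two things then push an uncorrected maximum-likelihood Wald z test towards too many false positives: the normal critical value is smaller than the t value, and maximum likelihood underestimates the between-clinic variance. A third works the other way. If health systems differ, stratified randomization balances them across arms, but a model without health system leaves their variance in the standard error, which makes the test more conservative.

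The plan fixes none of these. Its primary conclusion therefore rests on a test whose error rate could lie on either side of the intended level, and the confidence interval has the same problem. A result near the threshold could be called significant or not depending on a choice still open once the data are in.

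**Working it through.** **Inputs from the documents.** 30 clinics (33 recruited). About 3,960 patients in the Phase II aims table of section 8.0, so 3,960 / 30 = 132 per clinic; or about 4,500 in section 1.0, so 4,500 / 30 = 150. Minimum of 30 eligible patients per clinic (section 4.0).

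**Assumptions.** Two-sided 5% level; 1:1 allocation; ICC 0.01 to 0.10; control screening rate 10 to 35%; coefficient of variation (CV) of clinic size 0 or 0.6; three equal health systems in the stratified runs. The plan has no figure of its own to reproduce.

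**Step 1, analytic guide.** Let K be the number of clinics and q the number of clinic-level fixed effects.

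- Normal in place of t only: 2·P(T with K−q df > 1.96). With 27 or 28 df this is 6.0%.
- Adding the maximum-likelihood variance bias, a factor of about (K−q)/K: 2·P(T with K−q df > 1.96·√((K−q)/K)). For K = 30, q = 3 the cut-off is 1.96·√(27/30) = 1.859 on 27 df, which gives 7.4%. Without the baseline rate (q = 2) it is 6.9%. With K = 33 the two values are 7.1% and 6.7%.
- If two health-system terms were added (q = 5, assuming three systems) and the z test kept: 8.6% with 30 clinics, 8.2% with 33.

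This treats between-clinic variance as dominant, so simulation is the better guide.

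**Step 2, simulation under no effect.** Random-intercept logistic model fitted by maximum likelihood, 5,000 trials per row (simulation error about 0.3 to 0.4 points). Unless noted: 30 clinics, mean 132 patients, CV 0.6, control rate 20%, baseline rate in the model. The t reference uses clinics minus fixed effects as df (27 in most rows).

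| Setting | Wald z | Same SE, t reference |
|---|---|---|
| ICC 0.01 | 8.0% | 6.9% |
| ICC 0.03 | 8.1% | 6.8% |
| ICC 0.05 | 6.5% | 5.5% |
| ICC 0.10 | 7.4% | 6.2% |
| ICC 0.05, equal clinic sizes | 7.2% | 6.1% |
| ICC 0.05, no baseline rate | 6.7% | 5.5% |
| ICC 0.05, 33 clinics | 7.9% | 6.9% |
| ICC 0.05, control rate 35%, 150 per clinic | 7.5% | 6.2% |
| ICC 0.05, control rate 10% | 7.5% | 6.5% |
| ICC 0.05, stratified, systems carry 0% of between-clinic variance | 7.6% | 6.3% |
| ICC 0.05, stratified, systems carry 20% | 6.3% | 5.5% |
| ICC 0.05, stratified, systems carry 40% | 5.2% | 4.4% |

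In the last three rows health system is left out of the model, as planned. Counting only errors in favor of the intervention (nominal 2.5%), the z test gives 3.0 to 4.4% with no system effect, and 3.1% and 2.6% with a 20% and 40% share.

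**Step 3, agreement with other runs.**

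- A second set (2,500 trials per scenario, base rate 15 to 25%, ICC 0.02 to 0.10, no system effect) gave 7.0 to 8.5% for z and 5.5 to 6.9% for t with 27 df.
- A third (1,000 trials per scenario) gave 7.5 to 7.7% for z with no system effect, and 6.7% and 5.5% with systems carrying 20% and 40%.
- A 500-trial run with equal clinics at ICC 0.03 gave 5.4%. Its simulation error, √(0.054·0.946/500) = 1.0 point, is too large for it to separate 5% from 7%.

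**Step 4, a different fit under the same wording.** With restricted pseudo-likelihood at ICC 0.02 / 0.05 / 0.10 and no system effect, z rejects 7.2 / 6.4 / 5.5%. With five assumed systems carrying 20% it rejects 5.8 / 5.5 / 5.4%, and at 40%, 5.1 / 4.3 / 4.1%. With t on 27 df the last set becomes 4.2 / 3.5 / 3.6%, below nominal.

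**Step 5, effect on a borderline result.** A statistic of 2.0 gives p = 0.046 against z and 0.056 against t with 27 df. Allowing also for the variance bias, the maximum-likelihood statistic must reach 2.052·√(30/27) = 2.16, where the z p-value is 0.031. A default p-value between about 0.031 and 0.05 would therefore depend on a choice the plan does not make.

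**The case against.** The strongest reply is that the plan names no z test. A restricted fit with a t reference, or a permutation test, would satisfy the same sentence, and the 5% level is itself an assumption. A reader might infer that the plan prescribes a large-sample Wald test with a false-positive rate of 7 to 8.5%. The documents do not support that. They commit to no such test, and no fixed rate follows from the design: ordinary settings gave 6.5% and 6.7%, and leaving out an influential stratification factor brought the rate down to about 5%, or below 5% with a restricted fit. This part of the reply stands.

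It does not dispose of the point. Silence permits the anti-conservative test and allows the choice to be made after the data are seen. Nor can a reader infer that omitting health system makes the test safe. The offset needs systems to carry a substantial share of the between-clinic variance, which the documents do not show; if they carry none, the inflation remains in full. If they carry much, a t reference with system still omitted becomes conservative and loses power.

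It is also fair to say that preferring permutation to a well-corrected t test is partly a matter of judgment. Either would do if it is specified in advance and takes account of the strata.

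**Conclusion.** The concern holds as a gap in the primary test, not as a wrong test declared by the plan. With about 30 clinics, no stated small-sample method and the stratification factor left out of the model, the analysis as written has no assured error rate in either direction. Assuming a two-sided 5% level and an uncorrected maximum-likelihood Wald z test, the true error is roughly 6.5 to 8% if health systems do not differ and about 5 to 6.5% if they carry 20 to 40% of between-clinic variance. These ranges depend on the assumed ICC, screening rate, clinic-size variation and number of systems. The likely distortion is modest, but it falls on the trial's primary conclusion and is cheap to remove.

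**What to change.** In section 9.0, state that the primary p-value comes from a two-sided 5% permutation test of the arm effect that re-randomizes clinics within health-system strata, following the allocation procedure actually used. Such a test holds its level whatever the size of the system effect.

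Alternatively, specify a restricted (REML-type) fit that includes health system, a t reference with df equal to clinics minus clinic-level parameters, and a Kenward-Roger-type standard error. With the baseline rate and, say, three systems, the df would be 30 − 5 = 25. Use the same correction for the confidence interval.

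A t reference alone is not enough: with no system effect it still gave about 5.5 to 7%. Adding health-system terms while keeping the z test would make matters worse (8.6% in the analytic approximation).

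The cost is analysis-plan wording, a few lines of code and a small loss of nominal power relative to an uncorrected z test. Design, recruitment and data collection are unaffected.
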